6.3.2 Specimen Preparation, Specimen Handling and Storage

Whole blood will be collected and centrifuged at 2000 rpm for 10 minutes to separate plasma. Plasma will be frozen and stored at -20° C or lower until analysis.

6.3.3 Specimen Shipment

Naloxone samples will be transported in an ice packed Styrofoam container directly from CRU to our research lab (LRB/MTRF) by study personnel. At that point, they will be analyzed. Leftover samples will be stored in the freezer until all analysis is complete, then discarded. Counter regulatory hormones samples including glucagon, epinephrine, norepinephrine, and cortisol would be sent to the Vanderbilt Diabetes Research and Training Center Core Laboratory for analysis.

6.4 Clinical Procedures

6.4.1 Treatment Regimen

This study will consist of two 2-day intervention visits separated by approximately 8 weeks.

Subjects will be asked to report to the research center by 7 am on the first day of the study after fasting overnight. On arrival, intravenous lines will be placed in each arm (one will be used for infusions and the other for blood sampling). A minimum of 30 minutes after the IVs are placed, baseline blood samples will be drawn for later measurement of glucose, glucagon, epinephrine, norepinephrine, and cortisol. Subjects will then be given a 4 mg (0.1 ml) or 8 mg dose (0.2 mL of IN naloxone or a similar volume of IN placebo.. After naloxone or placebo dose, a hyperinsulinemic (2.0 mu/kg/min) hypoglycemic (target = 50 mg/dl) clamp protocol will be started. The clamp will be maintained for 2 hours. Blood samples will be collected every 5 minutes for monitoring of blood glucose levels and every 15 minutes during the last 90 minutes for later measurement of serum glucagon, epinephrine, norepinephrine and cortisol. If the subject received 4mg dose of IN naloxone or placebo, a second dose of 4 mg IN naloxone or placebo will be given at +30 min after the start of insulin clamp. Every 15 minutes during the last 90 minutes minutes of the morning clamp, subjects will be asked to quantitate their hypoglycemia related symptoms using a standardized questionnaire (12). At the completion of the morning clamp, glucose will be given to return the participant to normal glucose. 2 hours after the end of the morning clamp, a second 2 hour hyperinsulinemic (2.0 mu/kg/min) hypoglycemic (target = 50 mg/dl) clamp protocol will be started. At the start of this afternoon clamp study, a dose of 4 mg or 8 mg of IN naloxone or placebo will be given. Afternoon clamp will proceed as in the morning except that no serum or plasma will be collected except for the monitoring of glucose and collection of samples for subsequent measurement of naloxone. If the subject received 4 mg dose of intra-nasal naloxone or placebo, a second dose of 4 mg intra-nasal naloxone or placebo will be given after 30 minutes. After the completion of the afternoon clamp, subjects will be returned to euglycemia and fed a meal. They will then be allowed to leave the research center with instructions to return the next morning after an overnight fast. At 7 AM on day 2 they will undergo a single 2 hour hyperinsulinemic hypoglycemic clamp (target blood glucose 50 mg/dl) during which blood samples will be collected as on the morning of day 1. Symptom scores will be collected every 15 minutes during the last 90 minutes of the clamp. At the end of the study, infusions will be stopped, and participants will be fed a meal and then sent home after they are scheduled to return for Part 2 in 8 weeks. This timing is selected to ensure that female participants are studied at the same phase of the menstrual cycle; males will return for Part 2 in 8 ± 2 weeks. During Part 2 they will receive the treatment not provided during Part 1. The rest of the study protocol will be the same as in Part 1.

A description of the study visits is below:

V i s i t description	Expected activities	
Part 1 Day 1	 Randomization Morning (8 – 10 AM) hyperinsulinemic hypoglycemic clamp study with two, 4 mg doses of naloxone or placebo depending on randomization assignment, collection of counterregulatory hormones and hypoglycemia symptom scores. Afternoon (1 – 3 PM) hyperinsulinemic hypoglycemic clamp study with single 4 mg dose of naloxone or placebo depending on randomization assignment Meal 	
Part 1 Day 2	 Hyperinsulinemic hypoglycemic clamp study with collection of counterregulatory hormones and hypoglycemia symptom scores Lunch 	
8 week wash out period	• Usual activities	
Part 2 Day 1	 Morning (8 – 10 AM) hyperinsulinemic hypoglycemic clamp study with two 4 mg doses of naloxone or placebo depending on randomization assignment, collection of counterregulatory hormones and hypoglycemia symptom scores Afternoon (1 – 3 PM) hyperinsulinemic hypoglycemic clamp study with single 4 mg dose of naloxone or placebo depending on randomization assignment Meal 	
Part 2 Day 2	 Hyperinsulinemic hypoglycemic clamp study with collection of counterregulatory hormones and hypoglycemia symptom scores. Lunch 	

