The long-term goal of this project is to test the hypothesis that IN naloxone therapy in subjects with T1D and IAH will improve counter regulatory hormone responses during hypoglycemia and increase recognition of hypoglycemia symptoms. The purpose of this project is to evaluate IN naloxone as a therapy for the prevention and treatment of IAH. IAH can be reproduced experimentally by inducing recurrent hypoglycemia in healthy subjects (11), providing a robust investigational model for studying mechanism and treatments for IAH. In this study we will test the hypothesis that IN naloxone therapy will prevent the development of IAH in healthy subjects who are exposed to experimental hypoglycemia.

Rationale for route of administration, dose, and regimen: Intranasal delivery was selected in order to non-invasively produce similar naloxone concentrations to those attained from the IV dosing used in previous studies which demonstrated the beneficial effects of naloxone (9,10). Two, 4 mg doses, one to each nostril, administered 1 hr apart are expected to produce similar naloxone concentrations as a 0.4 mg/kg/mL dose administered over 90 minutes which was the dose used for the IV study (9). The half-life is reported to be 2.1 hours (Narcan package label) suggesting the drug will remain at elevated levels for ~ 4 hours (2 half-lives) after the second dose. A third 4 mg dose will be administered ~4 hrs after the second to remain levels similar to intravenous dosing. When a single 8 mg dose was administered to healthy volunteers, adverse events included increased blood pressure, musculoskeletal pain, headache, nasal dryness, nasal edema, nasal congestion, and nasal inflammation. These symptoms will be monitored throughout the study.

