6.3 Laboratory Testing Procedures

6.3.1 Frequency of Blood Draws

Three to five milliliter blood samples will be collected for determination of plasma naloxone concentrations prior to dosing, at 5 ± 1 , 15 ± 2 , 30 ± 3 minutes, and at 1.08 ± 5 , 1.5 ± 5 , 2, 3, 4, and 6 hours after completion of the first IN dose. The actual blood collection times for hours 2 through 6 may deviate by ± 10 minutes from the specified times. In all cases, the actual time of the blood draw will be recorded. Missed samples or breakage of a sample will be recorded.

Baseline blood samples will be drawn for glucose, glucagon, epinephrine, norepinephrine and cortisol before the dose of Naloxone or placebo and before the start of the insulin clamp. During the morning study on day 1, blood samples will be collected every 5 minutes for monitoring of blood glucose levels and every 15 minutes during the last 90 minutes of the clamp, for later measurement of serum glucagon, epinephrine, norepinephrine and cortisol. Afternoon clamp on day 1 will proceed as in the morning except that no serum or plasma will be collected except

for the monitoring of glucose and collection of samples for subsequent measurement of naloxone. On day 2 blood samples will be collected as on the morning of day 1.

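### The 1-hour spacing of the two morning 4 mg doses in the rationale matches the naloxone draw times, but the procedure gives 30 minutes plus an unstated lag, so the draws may miss the peak after the second dose

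*Combined protocol and SAP*

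**What the plan says.** Three places in the protocol bear on the timing of the second morning dose for participants on the 4 mg regimen.

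- Section 2.0, rationale for route, dose and regimen: "Two, 4 mg doses, one to each nostril, administered 1 hr apart are expected to produce similar naloxone concentrations", the comparator being the earlier intravenous regimen.
- Section 6.4.1, procedure: the first dose is given, then "After naloxone or placebo dose, a hyperinsulinemic (2.0 mu/kg/min) hypoglycemic (target = 50 mg/dl) clamp protocol will be started", and "a second dose of 4 mg IN naloxone or placebo will be given at +30 min after the start of insulin clamp". The second dose is timed from the clamp, not from the first dose. The wait between first dose and clamp start is not stated.
- Section 6.3.1, naloxone draws: before dosing, at 5 ± 1, 15 ± 2 and 30 ± 3 "minutes, and at 1.08 ± 5 , 1.5 ± 5 , 2, 3, 4, and 6 hours after completion of the first IN dose". All are timed from the first dose.

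Cmax and Tmax are named as secondary endpoints in the Study Summary and in Section 5.3.2. Section 5.1 gives naloxone first to up to 8 participants, partly to confirm that the intended concentrations are reached.

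**The concern.** The draw at 1.08 h is an unusual choice until it is read as 65 minutes, which is 5 minutes after a dose at 60 minutes; 1.5 h is then 30 minutes after it. The sampling grid appears to have been built for the interval in the rationale. The procedure does not secure that interval, and taken at face value (dose, then clamp, then second dose 30 minutes into the clamp) it gives something nearer half an hour.

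Two things are at stake. The exposure expectation in Section 2.0 may describe an interval different from the one delivered. And the draws meant to catch the rise and peak after the second dose may come too late, which affects observed Cmax and Tmax and the concentration check in the naloxone-first group. Because the lag is left open, the interval could also vary between participants who are all sampled on one fixed clock.

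**Working it through.** **Step 1: timeline.** Let g be the lag in minutes from first dose to clamp start. The second dose is at d = 30 + g. A draw scheduled at time t falls t − d minutes after it. The draws are at 5, 15, 30, 65 (1.08 × 60 = 64.8), 90, 120 and 180 minutes, then 4 and 6 h. The ± 5 on the 1.08 h and 1.5 h draws is read as minutes.

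| g | d | 30-min draw relative to dose 2 (window) | First scheduled draw after dose 2 (window) | Next draw |
|---|---|---|---|---|
| 0 | 30 | −3 to +3 | 35 (30 to 40) | 60 |
| 5 | 35 | −8 to −2 | 30 (25 to 35) | 55 |
| 10 | 40 | −13 to −7 | 25 (20 to 30) | 50 |
| 15 | 45 | −18 to −12 | 20 (15 to 25) | 45 |
| 30 | 60 | −33 to −27 | 5 (0 to 10) | 30 |

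At g = 30 the interval is exactly 1 hour and all three sections agree. The first scheduled draw is more than 30 minutes after the second dose only if g is below 5.

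**Step 2: what the documents imply about g.** Participants arrive by 7 am ("Subjects will be asked to report to the research center by 7 am on the first day of the study"), and "A minimum of 30 minutes after the IVs are placed, baseline blood samples will be drawn". The visit table gives "Morning (8 – 10 AM) hyperinsulinemic hypoglycemic clamp study with two, 4 mg doses". For g = 30 with an 8 AM clamp, the first dose is at 7:30, so both lines must be in by 7:00. Early arrival allows that, but nothing requires it. The afternoon first dose is given at clamp start and the second 30 minutes later, and that session is described as running like the morning. This points to a short lag without settling it.

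**Step 3: effect on morning Cmax.** The documents give no single-dose Tmax, so 10 to 45 minutes is assumed. The half-life of 2.1 h (126 min) is from Section 2.0. The model has one compartment with first-order absorption:

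- ke = ln 2 / 126 = 0.0055 per min;
- ka solves Tmax = ln(ka/ke)/(ka − ke), giving 0.445, 0.263, 0.180, 0.103 and 0.058 per min for Tmax of 10, 15, 20, 30 and 45 min;
- one dose gives C(t) proportional to exp(−ke·t) − exp(−ka·t), and the total is C(t) + C(t − d).

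The shortfall is 1 − (largest value at the draw times up to 180 min) / (true maximum before the afternoon dose).

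| Draws | Interval d | Tmax 10 | 15 | 20 | 30 | 45 |
|---|---|---|---|---|---|---|
| Current | 30 (g = 0) | 12.4% | 9.7% | 6.9% | 2.3% | 0.0% |
| Current | 45 (g = 15) | 4.9% | 2.2% | 0.4% | 0.6% | 1.2% |
| Current | 60 (g = 30) | 3.3% | 7.1% | 4.3% | 0.7% | 0.5% |
| 65 and 90 min moved to d + 15 and d + 30 | 30 | 2.3% | 0.3% | 0.1% | 0.8% | 0.7% |
| Same | 45 | 2.3% | 0.3% | 0.2% | 0.8% | 0.5% |
| Same | 60 | 2.2% | 0.3% | 0.2% | 0.7% | 0.5% |

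At zero lag the true peak lies at about 39 to 66 minutes while the recorded Tmax is 65 in all five cases. At a 15-minute lag the recorded Tmax is 65 in four cases and 90 in the fifth (Tmax 45).

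**The case against.** A reader might infer that the trial doses at 30 minutes, and that no draw is scheduled in the half hour after the second dose. The documents do not establish either. The procedure fixes the second dose relative to the clamp and leaves the lag open; a 30-minute lag is compatible with the clock times and would remove the conflict entirely. The 12% figure belongs to one corner of the range, zero lag with a 10-minute Tmax. The fair comparator is the same grid at the interval it fits, where the model already loses up to about 7%. Against that comparator the 30-minute interval costs roughly 9, 3, 3 and 2 points more for Tmax of 10, 15, 20 and 30, and nothing more at 45.

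The consequence is also limited. Section 6.4.3 defines Cmax as the maximum observed concentration without confining it to the morning, and the results are summarised descriptively. The primary endpoint is epinephrine and does not use these draws. Actual draw times (Section 6.3.1) and dose times (Section 9.3) are recorded, and the planned compartmental and population models can use them.

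All of this stands, and it rules out calling the schedule a demonstrated sampling failure. It does not remove the gap. The rationale and the draw grid rest on an interval that the procedure does not specify, and non-compartmental Cmax and Tmax are read directly from the observed draws, so modelling compensates only in part.

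**Conclusion.** The point holds as an unreconciled interval with a conditional effect on sampling. Section 2.0 and the draw times in Section 6.3.1 fit 1 hour; Section 6.4.1 gives 30 minutes plus an unstated lag, and the surrounding text favours a short one. With a lag under 5 minutes the 30-minute draw sits on or close to the second dose, the next scheduled draw is more than 30 minutes after it, and modelled morning Cmax is low by up to 12%, depending on how fast absorption is. At longer lags the loss is smaller but not zero.

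These percentages rest on a one-compartment model, equal doses, draws at their scheduled times and an assumed Tmax range. They show scale and are not estimates for this product. Participants given a single 8 mg morning dose are unaffected, and the documents do not say what share of participants that is. The change is worth making because it costs little and improves a named secondary endpoint. The validity of the primary comparison is not in question here. No view is taken on which dose interval is right.

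**What to change.** 1. Reconcile Sections 2.0, 6.3.1 and 6.4.1 on the morning 4 mg interval. The sponsor decides which stands. State the time from first dose to clamp start, and make the exposure expectation in Section 2.0 refer to the interval actually used.
2. In Section 6.3.1, for 4 mg participants, time the draws that follow the second dose from its recorded time. If the 30-minute draw coincides with that dose, take it just before. Move the 1.08 h and 1.5 h draws to 15 and 30 minutes after the second dose. The 15-minute draw matters most: the current pair at a 1-hour interval, 5 and 30 minutes after the dose, still loses up to 7.1% in the model.
3. Leave the draw times for participants on a single 8 mg morning dose as they are.

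The cost is protocol wording and a revised draw sheet, with no added sample. The modelled Cmax loss is then about 2% at most for intervals of 30, 45 or 60 minutes. There are two small downsides. Participants already sampled keep the old times, which the compartmental model can accommodate. And in the slowest-absorption case at zero lag the loss rises from 0.0% to 0.7%.

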5.0 Study Design

5.1 Overview of Study Design

This is a single center, single-blind randomized cross over design trial that will compare the impact of intra-nasal naloxone vs. intra-nasal placebo administration during experimental hypoglycemia on day one vs. day two. We intend to enroll 18 individuals to obtain the complete data sets from 15 participants. Initially up to 8 of these subjects will receive intra-nasal naloxone first prior to placebo in order to evaluate tolerability and to ensure that the desired drug concentrations are achieved. Double-blinding is not possible because we will not be able to replicate for the placebo (placebo) the same delivery device as is being provided by the manufacturer for the naloxone; the manufacturer is unable to provide placebo-charged devices for us to use as placebo. Our own labeling will be put over both naloxone and placebo devices in order to obscure any device labeling that would break the blind for the participant. Expected duration of subject participation is 10-12 weeks. This study will consist of two 2-day intervention visits separated by approximately 8 weeks.

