5.4.5 Inclusion Criteria

Subjects will be eligible to participate in the study if all of the following conditions exist:

- 1. Males and females between the ages of 18-65 years.
- 2. Subjects are capable of giving informed consent.
- 3. Female subjects must be post-menopausal for at least 1 year, or surgically incapable of bearing children, or practicing at least one or more of the following methods of contraception for three months prior to, and during the study: hormonal, intrauterine device (IUD), or barrier method in combination with a spermicide.
- 4. Subject should be medication free, other than hormonal birth control, for 48 hours before through 24 hours after study drug administration. If the need for medication is identified during this time period, it will be discussed with and approved by the PI.

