7.2 Statistical Methods

Our primary outcome is the peak epinephrine response during the third hypoglycemic clamp of each infusion experiment, thus each participant will have two observations: one from their naloxone experiment and one from their placebo experiment. We will fit a general linear mixed model with fixed effects for treatment (Naloxone vs. placebo), treatment order (Naloxone first vs. placebo first), and period (Part 1 vs. Part 2) and a random effect for participant. We are confident that our study design, with a washout period of 8 weeks between Parts 1 and 2, has minimized the possibility of a treatment effect from Part 1 that lingers into Part 2. We will also consider adjustment for important baseline characteristics, such as age and sex. Diagnostics will be examined to assess model assumptions.

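### An 8-week return makes the same menstrual phase likely only for cycles near 28 days; it does not ensure it, and cycle day is not recorded

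*Combined protocol and SAP*

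**What the plan says.** Section 6.4.1 has participants "then sent home after they are scheduled to return for Part 2 in 8 weeks" and gives the reason: "This timing is selected to ensure that female participants are studied at the same phase of the menstrual cycle". It then sets a separate rule for men: "males will return for Part 2 in 8 ± 2 weeks". Section 5.1 describes "two 2-day intervention visits separated by approximately 8 weeks", and the visit table in Section 6.4.1 lists an "8 week wash out period". No window is stated for women.

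The inclusion criteria (Section 5.4.5) read: "Female subjects must be post-menopausal for at least 1 year, or surgically incapable of bearing children, or practicing at least one or more" of the listed contraceptive methods, which are "hormonal, intrauterine device (IUD), or barrier method in combination with a spermicide". A woman using a barrier method is therefore eligible with a natural cycle. Neither the inclusion nor the exclusion criteria mention cycle length or regularity. Screening (Section 5.4.3) and the items listed for the case report form (Section 9.3) do not mention last menses or cycle day. On covariates, Section 7.2 says only: "We will also consider adjustment for important baseline characteristics, such as age and sex".

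**The concern.** By choosing the interval for this reason, the protocol treats cycle phase as a nuisance factor worth controlling. The control it adopts is a calendar interval, which returns a woman to the same point of her cycle only if 56 days is a whole number of her own cycles. The plan sets no cycle-length criterion, keeps no record of cycle day and includes no phase term. A mismatch would therefore be neither prevented nor detected nor available for adjustment.

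Naloxone and placebo are compared between Part 1 and Part 2 within the same person. A change of phase between parts can therefore add variation to that person's treatment contrast, in a trial planned on 15 completers. Cycle day not noted at the visit may also be hard to recover later.

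**Working it through.** **Inputs.** The interval is 8 weeks, that is 8 × 7 = 56 days (Section 6.4.1). Cycle length L is not given in the documents; I assume 21 to 35 days to show the range.

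**When is the shift zero?** Only if L = 56/k for a whole number k: 56, 28 or 18.7 days for k = 1, 2, 3. Within 21 to 35 days, only 28 qualifies.

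**Size of the shift.** Let d be the distance from 56 to the nearest multiple of L. To show what d means for broad phases, suppose Part 1 falls on a random cycle day and the cycle has two equal halves (both are assumptions). The chance that both parts fall in the same half is then 1 − 2d/L.

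| L (days) | Nearest multiple | d (days) | d/L | Chance of same half |
|---|---|---|---|---|
| 21 | 63 | 7 | 33% | 0.33 |
| 22 | 66 | 10 | 45% | 0.09 |
| 24 | 48 | 8 | 33% | 0.33 |
| 26 | 52 | 4 | 15% | 0.69 |
| 27 | 54 | 2 | 7% | 0.85 |
| 28 | 56 | 0 | 0% | 1.00 |
| 29 | 58 | 2 | 7% | 0.86 |
| 30 | 60 | 4 | 13% | 0.73 |
| 32 | 64 | 8 | 25% | 0.50 |
| 35 | 70 | 14 | 40% | 0.20 |

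If the 8 weeks are counted from Day 2 of Part 1, the interval from Day 1 to Day 1 is 57 days, and even a 28-day cycle shifts by 1 day.

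**How a shift reaches the outcome.** Write g(c) for an additive effect of cycle day c on peak epinephrine, with c_N and c_P the cycle days on the first morning of the naloxone and placebo parts.

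- Third-clamp peak (Section 7.2), measured on Day 2: the naloxone minus placebo contrast contains g(c_N + 1) − g(c_P + 1). A mismatch enters in full.
- Day 1 to day 2 difference (Sections 4.1 and 5.3.1): the contrast contains [g(c_N) − g(c_N + 1)] − [g(c_P) − g(c_P + 1)]. The two mornings are one day apart, so each bracket is near zero if g changes little from one day to the next. What remains is any effect of phase on the amount of blunting itself.

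**Room for extra noise in the plan's power statement.** Section 5.4.1 states 85% power for 157 pg/ml with 15 completers, one-sided 5%, and an SD of the paired difference up to 216 pg/ml. A paired t calculation gives power 0.849 and a maximum SD of 215.5, so the statement reproduces. The plan's SD table also reproduces: 170 × √(2 × 0.8) = 215 at ρ = 0.2 and 170 × √(2 × 0.6) = 186 at ρ = 0.4. Independent extra noise that would bring the total to 216:

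- from 215: √(216² − 215²) = √431, about 21 pg/ml;
- from 186: √(216² − 186²) = √12,060, about 110 pg/ml.

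These figures show how much room there is. They do not estimate a phase effect, for which the documents give no value.

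**The case against.** The case on the other side has real force on consequences, less on the claim itself.

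- *Phase is not cycle day.* The protocol promises the same phase. A reader might infer that matching is lost for every cycle other than 28 days. That goes too far: a shift of 2 to 4 days often stays within a broad phase, and on the two-half assumption the chance is about 0.85 at 27 or 29 days and 0.73 at 30. Nor is 14 days in a 35-day cycle the opposite phase, since half of that cycle is 17.5 days.
- *No systematic bias.* Up to 8 participants take naloxone first by design (Section 5.1), so a reader might infer a shift that order does not balance. The documents do not support this. The direction of the shift depends on whether a woman's cycle is shorter or longer than 28 days, and its effect depends on the cycle day of Part 1, which the plan does not fix. A common difference between parts would be taken up by the period term in the Section 7.2 model.
- *The endpoint may remove most of it.* This stands for the day 1 to day 2 difference, but not for the third-clamp outcome named in Section 7.2.
- *Approximately 8 weeks leaves room.* Section 5.1 and the opening of Section 6.4.1 could accommodate scheduling by cycle. No procedure for this is written, however, and the only stated window is for men.
- *Few may be affected.* Men and post-menopausal women are unaffected, and women on hormonal contraception may not have a natural cycle. The documents do not give the number of naturally cycling women.

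These points limit the size of the problem. They do not make a calendar rule ensure the same phase.

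**Conclusion.** The point holds as a modest one. The schedule makes phase matching likely near 28 days and progressively less certain away from it, and nothing else in the plan supplies or checks the property claimed. The cost is avoidable within-person noise in naturally cycling women. How much of it reaches the analysis depends on which of the plan's two outcome definitions is used.

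The day shifts rest on the assumed cycle range. The conclusion needs only that some enrolled women have cycles that differ from 28 days or are irregular. Without a phase effect on epinephrine, a sex split or a count of women with natural cycles, the loss of power cannot be stated. This is a worthwhile improvement, not a threat to the trial's validity.

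**What to change.** For women with natural cycles, schedule Part 2 two of their own cycles after Part 1, at the same cycle day within a few days. Two cycles of 21 to 35 days span 2 × 21 = 42 to 2 × 35 = 70 days, which is exactly the 6 to 10 weeks already accepted for men. State this window for these women in Section 6.4.1 and record cycle day at both parts on the case report form. Keep the calendar rule for men, post-menopausal women and hormonal-contraceptive users.

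The cost is some scheduling flexibility, one recorded date per part and a slightly variable interval between parts.

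If scheduling is not changed, replace the word *ensure* with wording that a calendar rule can support, and record cycle day at both parts so that a sensitivity analysis is possible.

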Version #	Version Date	Significant Changes from Previous Version
01	02/03/2016	Original Protocol Version
02	04/25/2016	Added additional justification for sample size
03	06/28/2016	Change randomization for the first 3 subjects to naloxone
04	01/05/2017	Add 8mg dose of naloxone; change randomization for the first 8 subjects to naloxone
05	01/31/2019	Update study location

Table of Contents

List of Abbreviations	.6
1.0 Study Contact Information	.7
2.0 Introduction / Background and Rationale	.8

Study Summary

Title	Intra-nasal Naloxone for treatment of impaired awareness of hypoglycemia
Short Title	Intra-nasal Naloxone for impaired awareness of hypoglycemia
IRB Number	1603M84961
Study Sponsor	[name]
Phase	1
Principal Investigator	[name]
Study Design	Single center, single-blind, randomized, cross-over
Study Duration	24 months
Study Center(s)	Clinical Research Unit (CRU)
Objectives	Primary Objective: To evaluate intra-nasal Naloxone as a therapy for prevention and treatment of impaired awareness of hypoglycemia.
	Secondary Objective: Characterize naloxone pharmacokinetics following multiple administrations.
Number of Subjects	18
Main Inclusion Criteria	Males and females between the ages of 18-65 years
Study Product, Dose, Route, Regimen	Narcan (naloxone hydrochloride) intranasal spray, 4 mg/nostril repeated 4 times within 8 hours alternating nostrils.
Duration of Administration	4 doses of 4 mg or 2 doses of 8 mg administered over 1 day.
Endpoints	Primary endpoint will be the within person difference in peak epinephrine secretion during the morning episodes of hypoglycemia on days one and two; we will compare this difference between the two treatment conditions.
	Secondary endpoint will be naloxone pharmacokinetics including maximum concentration (Cmax), time to maximum concentration (Tmax) and area under the curve (AUC).
Statistical Methods	We will fit a general linear mixed model with fixed effects for treatment (naloxone vs. placebo), treatment order (naloxone first vs. placebo first), and period (Part 1 vs. Part 2) and a random effect for participant. We will also consider adjustment for important baseline characteristics, such as age and sex. Diagnostics will be examined to assess model assumptions.

List of Abbreviations

AE	Adverse Event	
CFR	Code of Federal Regulations	
CRF	Case Report Form	
DSMB	Data and Safety Monitoring Board	
DSMP	Data and Safety Monitoring Plan	
FDA	Food and Drug Administration	

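### Section 6.4.1 contradicts itself on day 1 dosing and timing: its text gives 16 mg and a 2 h gap between clamps, its visit table 12 mg and a 3 h gap

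*Combined protocol and SAP*

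**What the plan says.** **Section 6.4.1, text.** A first dose of 4 mg or 8 mg precedes the morning clamp. For participants on 4 mg, "a second dose of 4 mg IN naloxone or placebo will be given at +30 min after the start of insulin clamp". The afternoon session is timed from the end of the morning one: "2 hours after the end of the morning clamp, a second 2 hour hyperinsulinemic" clamp begins. At its start, "a dose of 4 mg or 8 mg of IN naloxone or placebo will be given", and for participants on 4 mg, "a second dose of 4 mg intra-nasal naloxone or placebo will be given after 30 minutes".

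**Section 6.4.1, visit table.** For Day 1 of both Parts, the morning entry (8 to 10 AM) is a "hyperinsulinemic hypoglycemic clamp study with two, 4 mg doses of naloxone or placebo depending on randomization assignment". The afternoon entry (1 to 3 PM) is a "hyperinsulinemic hypoglycemic clamp study with single 4 mg dose of naloxone or placebo". An 8 mg dose appears nowhere in the table.

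**Elsewhere.**
- The Study Summary's duration row gives "4 doses of 4 mg or 2 doses of 8 mg administered over 1 day", and Section 3.2.2 gives the same two regimens.
- The Study Summary's product row gives only "4 mg/nostril repeated 4 times within 8 hours alternating nostrils".
- The rationale in Section 2.0 describes two 4 mg doses 1 h apart and a third about 4 h after the second. It mentions no fourth dose and no 8 mg regimen for this trial.
- Section 6.6 supplies no separate timetable; it refers back to 6.4.1.

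**The concern.** Both versions are current text in the section that serves as the schedule of events, and nothing says which prevails. Staff who follow one depart from the other. What differs is how much study drug healthy volunteers receive in the afternoon of day 1, and when.

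Several procedures hang on the doses. Section 6.4.2 ties blood pressure and pulse checks to each dose. Section 6.7 counts the required 3 h stay from the last dose. Section 6.3.1 fixes the naloxone samples relative to the first dose, so a later afternoon dose changes what the last samples measure. If the two versions were used for different participants, their exposure and their late concentrations would not be directly comparable, and the secondary endpoint is pharmacokinetic.

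**Working it through.** **Dose totals** (number of doses × dose size)

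| Source | Morning | Afternoon | Day 1 total |
|---|---|---|---|
| 6.4.1 text, 4 mg regimen | 2 × 4 = 8 mg | 2 × 4 = 8 mg | 16 mg |
| 6.4.1 text, 8 mg regimen | 1 × 8 = 8 mg | 1 × 8 = 8 mg | 16 mg |
| 6.4.1 visit table | 2 × 4 = 8 mg | 1 × 4 = 4 mg | 12 mg |
| Study Summary duration row; 3.2.2 | not split | not split | 4 × 4 = 16 mg or 2 × 8 = 16 mg |
| Section 2.0 rationale | not split | not split | 3 × 4 = 12 mg |

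The text therefore reproduces the Study Summary's 16 mg and the table does not. The difference is 16 − 12 = 4 mg, or 4/16 = 25% of the total. All of it falls in the afternoon, where 4 mg is half of 8 mg.

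**Gap between clamps.** Text: 2 h. Table: 10 AM to 1 PM = 3 h. Run-in time does not explain the extra hour. The text describes a 2 h clamp with hormone samples over its last 90 minutes, and the table's windows are also 2 h long.

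**Can the rationale decide the gap?** The second morning dose comes 0.5 h into a 2 h clamp, so 1.5 h of the clamp remains. The next dose is at the start of the afternoon clamp.
- Text gap: 1.5 + 2 = 3.5 h after the second dose.
- Table gap: 1.5 + 3 = 4.5 h after the second dose.

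The rationale's figure of about 4 h lies midway, so it selects neither.

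**Naloxone samples.** Let L be the lead, in hours, of the first dose before the morning clamp; 6.4.1 does not state it. Assume the table's single afternoon dose is given at clamp start, as in the text (the table does not say).

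| | Text | Table |
|---|---|---|
| First afternoon dose, h after first dose | L + 2 + 2 = L + 4 | L + 2 + 3 = L + 5 |
| 4 h sample, h before that dose | L | L + 1 |
| 6 h sample, h after that dose | 2 − L | 1 − L |

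The shift is 1 h for any L. If L is taken as 0.5 h (first two doses 1 h apart, as in Section 2.0, with the second at +30 min), the 4 h sample is 0.5 h or 1.5 h before the first afternoon dose, and the 6 h sample is 1.5 h or 0.5 h after it.

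**Dose-linked checks.** At two per dose (before, and about 30 minutes after), day 1 has 4 × 2 = 8 (text, 4 mg), 2 × 2 = 4 (text, 8 mg) or 3 × 2 = 6 (table), not counting the check before discharge. Some may coincide.

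**Required stay.** Under the text's 4 mg regimen the last dose is 0.5 h into the afternoon clamp, so the stay ends 0.5 + 3 = 3.5 h after clamp start. It ends at 3.0 h under the text's 8 mg regimen and, on the same assumption about the single dose, at 3.0 h under the table.

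**The case against.** The strongest reply is that the table is only an outline of the visits, while the text is the step-by-step procedure. The Study Summary's duration row and Section 3.2.2 both support the text's dose count. A unit supplied with four 4 mg doses would notice that the table uses three, so nobody need follow the table alone. The documents indeed do not show that anyone would.

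That lowers the chance of an error but does not remove the conflict. Leaving out the 8 mg regimen could pass as brevity; stating that there is one afternoon dose cannot, because it is a specific count that disagrees with the text. The rationale in Section 2.0 also has three doses, so the rest of the protocol is not uniformly on the text's side.

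Parts of the reply do stand:
- The checks in 6.4.2 and the stay in 6.7 are worded per dose and from the last dose, so they adjust to whichever schedule is used. The number of checks already varies from 4 to 8 between the text's own two regimens. These are consequences to verify, not separate contradictions.
- Draw and dose times are recorded (6.3.1, 9.3), and the compartmental and mixed-effects modelling in 6.4.3 can use actual times. The 1 h shift costs consistency between participants, not data.
- The Study Summary's product row agrees with the text on 16 mg and is merely incomplete, since the next row adds the 8 mg regimen.

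**Conclusion.** The contradiction is real and must be fixed. Within 6.4.1, day 1 is 16 mg by the text and 12 mg by the table, the afternoon amount is 8 mg or 4 mg, the 8 mg regimen is present or absent, and the gap between clamps is 2 h or 3 h. The dose figures need no assumption. The 3 h gap rests on the table's clock times read as clamp start and end. The 1 h shift of the 4 h and 6 h samples, and the table's 3.0 h for the stay, also assume that the table's single afternoon dose is given at clamp start.

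The primary model is unaffected, and the sample-size calculation uses neither dose nor timing. The importance lies in how much drug volunteers receive and when, and secondarily in the comparability of late naloxone concentrations. Nothing here implies that either schedule is the right one.

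**What to change.** Reconcile the Study Summary (product and duration rows), Section 2.0, Section 3.2.2, and the text and visit table of Section 6.4.1, so that they state one dose count, dose size and interval between clamps for each regimen in use. Show every such regimen in the visit table, for both Parts, with the time of each dose relative to clamp start, including the first morning dose.

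Then check that the sampling times in 6.3.1, the dose-linked checks in 6.4.2 and the stay in 6.7 fit the reconciled schedule. The choice of schedule belongs to the investigators.

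The cost is amendment wording. The reconciliation itself needs no new data collection, no change to the sample size and no change to the primary model. If the check of 6.3.1 shows that a sampling time no longer fits, that time would have to be amended as well.
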